3.3 Study Population

For entry into the study, the following criteria MUST be met.

3.3.1 Inclusion Criteria

1. Signed Written Informed Consent

- a. Subject is willing to participate and has signed informed consent.

2. Target Population

- a. Subjects must meet the proposed 2015 ACR/EULAR Classification Criteria for SS (Sjögren’s Syndrome) ([Appendix 3](#)), as specified for pSS (primary Sjögren’s Syndrome).

- i. If a prior labial salivary or parotid gland biopsy was performed, information will be reported in the CRF and the report should be obtained for the source documents.
- b. Subjects should have pSS that is refractory to symptomatic or local therapy (eg, NSAIDs).
- c. ESSDAI \geq 5 at screening.
- d. Positive anti-SSA/Ro at screening.
- e. Stimulated salivary flow of at least 0.1 mL/min at screening and randomization in at least 124 subjects (72%). Enrollment of subjects with less than 0.1 mL/min of stimulated salivary flow at screening and/or randomization may be closed after 48 of such subjects are randomized.
- f. Subject Re-enrollment: This study permits the re-enrollment of a subject that has discontinued the study as a pre-treatment failure (ie, a “screen failure”, the subject has not been randomized / has not been treated). If re-enrolled, the subject must be re-consented and will receive a new PID.

3. Age and Reproductive Status

- a. Males and Females, ages \geq 18 (or age of majority).
- b. Women of childbearing potential (WOCBP) must have a negative serum or urine pregnancy test (minimum sensitivity 25 IU/L or equivalent units of HCG) within 24 hours prior to the start of study drug.
- c. Women must not be breastfeeding.
- d. Women of childbearing potential (WOCBP) must agree to follow instructions for method(s) of contraception for the duration of treatment with study drug(s) (abatacept/placebo) plus 5 half-lives of study drug (70 days) plus 30 days (duration of ovulatory cycle) for a total of 100 days post-treatment completion.
- e. Males who are sexually active with WOCBP must agree to follow instructions for method(s) of contraception for the duration of treatment with study drug(s) (abatacept/placebo) plus 5 half-lives of the study drug (70 days) plus 90 days (duration of sperm turnover) for a total of 160 days post-treatment completion. In addition, male subjects must be willing to refrain from sperm donation during this time.
- f. Azoospermic males are exempt from contraceptive requirements. WOCBP who are continuously not heterosexually active are also exempt from contraceptive requirements, and still must undergo pregnancy testing as described in this section.

Investigators shall counsel WOCBP, and male subjects who are sexually active with WOCBP, on the importance of pregnancy prevention and the implications of an unexpected pregnancy. Investigators shall advise on the use of highly effective methods of contraception ([Appendix 1](#)), which have a failure rate of $< 1\%$ when used consistently and correctly.

3.3.2 Exclusion Criteria

1. Target Disease Exceptions

- a. Subjects who have a systemic autoimmune disease other than Sjögren's syndrome (SS), such as RA, SLE, or systemic sclerosis, that can better explain the majority of the symptoms (ie, secondary Sjögren's syndrome).
- b. Subjects who have another autoimmune disease or inflammatory condition that could interfere with assessment of response of primary SS (pSS) to therapy (eg, systemic sclerosis, inflammatory bowel disease, gout).
- c. Subjects with any other medical condition associated with clinical features overlapping those of pSS or that would interfere with interpretation of results, including but not limited to a history of head and neck radiation treatment, sarcoidosis, amyloidosis, graft-versus-host disease, hepatitis C, acquired immunodeficiency syndrome, and IgG4-related disease.
- d. Subjects with severe fibromyalgia that could interfere with the assessment of response of pSS to therapy.
- e. Active life-threatening or organ-threatening complications of SS disease at the time of screening based on investigator evaluation including but not restricted to the following:
 - i. Vasculitis with renal, digestive, cardiac, pulmonary or central nervous system (CNS) involvement characterized as severe (note: cutaneous vasculitis is allowed)
 - ii. Active CNS or peripheral nervous system (PNS) involvement requiring high dose steroids
 - iii. Severe renal involvement, eg, GFR < 60 mL/min, a serum creatinine > 2 mg/dL, or proteinuria > 3 g/day,
 - iv. Severe pulmonary involvement, eg, shortness of breath at rest, or pulmonary function tests demonstrating DLCO < 40% or FVC < 60%
 - v. Severe muscular involvement requiring high dose steroids
 - vi. Lymphoma

2. Medical History and Concurrent Diseases

- a. Subjects at risk for tuberculosis (TB) defined as follows:
 - i. Current clinical, radiographic or laboratory evidence of active TB, even if currently being treated. Chest x-rays (posterior/anterior and lateral) obtained within the 6 months prior to screening and TB testing (IFN- γ release assay or PPD) performed in the past month prior to screening will be accepted; however, a copy of the reports must be placed in the subject binder.
 - ii. A history of active TB unless there is documentation that the subject had received prior anti-TB treatment that was appropriate in duration and type according to local health authority guidelines.

- iii. Subjects with a positive TB screening test indicative of latent TB will not be eligible for the study unless they:
 - 1. Have no evidence of current TB based on chest x-ray performed during the screening period and by history and physical exam, and
 - 2. They are currently being treated for latent TB or the site has documentation of successful prior treatment of latent TB. Treatment regimens should be dictated by local guidelines as long as the treatment dose and duration meet or exceed local health authority guidelines. If permitted by local guidelines regarding treatment with biologic medications, subjects with latent TB may be randomized prior to completion of treatment as long as they have completed at least 4 weeks of treatment and they have no evidence of current TB on chest x-ray at screening.
- b. Subjects with recent acute infection defined as:
 - i. Any acute infection within 60 days prior to randomization that required hospitalization or treatment with parenteral antibiotics.
 - ii. Any acute infection within 30 days prior to randomization that required oral antimicrobial or antiviral therapy.
- c. Subjects with history of chronic or recurrent bacterial infection (such as chronic pyelonephritis, osteomyelitis, and bronchiectasis etc.).
- d. Subjects who have a history of systemic fungal infections (such as histoplasmosis, blastomycosis, or coccidiomycosis).
- e. Subjects with history of recurrent herpes zoster (more than 1 episode) or disseminated (more than 1 dermatome) herpes zoster or disseminated herpes simplex, or ophthalmic zoster will be excluded. Symptoms of herpes zoster or herpes simplex must have resolved more than 60 days prior to screening.
- f. Subjects with history of Human Immunodeficiency Virus (HIV) infection or who test positive for HIV at screening.
- g. Subjects with a history of primary immunodeficiency.
- h. Subjects who have a present malignancy or previous malignancy within the last 5 years prior to screening (except documented history of cured non-metastatic squamous or basal cell skin carcinoma or cervical carcinoma in situ). Subjects who had a screening procedure that is suspicious for malignancy, and in whom the possibility of malignancy cannot be reasonably excluded following additional clinical, laboratory or other diagnostic evaluations. Subjects with a history of lymphoma
- i. Current clinical findings of severe, progressive, or uncontrolled renal, hepatic, hematological, gastrointestinal, pulmonary, psychiatric, cardiac, endocrine, neurological, or cerebral disease including severe and uncontrolled infections, such as sepsis and opportunistic infections. Concomitant medical conditions that, in the opinion of the investigator, might place the subject at unacceptable risk for participation in this study.
- j. Subjects who have received any live vaccines within 3 months of the study drug administration or are scheduled to receive live vaccines during the study. Study subjects should not be administered a live virus vaccine for a minimum of 3 months

following the last dose of study medication. Subjects who are in close contact with others who have received a live vaccine may be enrolled at the investigator's discretion.

- k. Subjects who have undergone a major surgical procedure within the 60 days prior to randomization.
- l. Subjects with a history of (within 12 months of signing informed consent), or known current problems with drug or alcohol abuse history or known cirrhosis including alcoholic cirrhosis.
- m. Subjects who are impaired, incapacitated, or incapable of completing study-related assessments.

3. Physical and Laboratory Test Findings

- a. Hepatitis B surface antigen (HBsAg)-positive, *or* hepatitis B core antibody (HBcAb)-positive subjects with detectable hepatitis B viral DNA, *and* where required by local regulations or standard practice hepatitis B surface antibody (HBsAb)-positive subjects with detectable hepatitis B viral DNA.
- b. Hepatitis C antibody (HcAb)-positive subjects with detectable hepatitis C viral RNA
- c. Hemoglobin (Hgb) < 8.5 g/dL
- d. White Blood Count (WBC) < 2,500/mm³ (2.5×10^9 /L)
- e. Lymphocytes < 500/mm³ (0.5×10^9 /L)
- f. Platelets < 50,000/mm³ (50×10^9 /L)
- g. Subjects with serum ALT or AST > 3 times upper limit of normal unless in the judgment of the investigator the elevation is explicitly related to pSS and does not pose a risk to participation in the study.
- h. Any test results that, in the opinion of the investigator, might place the subject at unacceptable risk for participation in this study.

4. Allergies and Adverse Drug Reaction

- a. Hypersensitivity to abatacept and/or its excipients

5. Prohibited Treatments and/or Therapies

- a. Subjects who have previously been exposed to abatacept or anti-CD28 therapy.
- b. Subjects who have received IV, IM, SC or intra-articular corticosteroids within 4 weeks of randomization (Day 1).
- c. Subjects who have taken rituximab within 12 months prior to randomization (Day 1).
- d. Subjects who have taken belimumab within 12 weeks prior to randomization (Day 1).
- e. Subjects who have taken a biologic therapy other than rituximab or belimumab or any other investigational therapy within 12 weeks or 5 half-lives prior to randomization (Day 1), whichever is longer.
- f. Subjects who have taken cyclophosphamide, mycophenolate mofetil (MMF)/mycophenolic acid (MPA) or leflunomide within 6 months of randomization (Day 1).
- g. Subjects who have taken methotrexate within 12 weeks of randomization (Day 1).

- h. Subjects who have taken cyclosporine (systemic), azathioprine, tacrolimus, tofacitinib, mizoribine, actarit, or bucillamine within 4 weeks of randomization (Day 1).
- i. Subjects who have taken Intravenous Immunoglobulin (IVIG) within 4 weeks of randomization (Day 1).
- j. Subjects who have taken diquafosol or ophthalmic rebamipide within 4 weeks prior to randomization (Day 1).
- k. Subjects who have taken a tricyclic antidepressant drug within 4 weeks prior to randomization (Day 1).
- l. Subjects are not permitted to have new installation of lacrimal punctum plugs within 4 weeks of randomization (Day 1). Subjects with existing lacrimal punctum plugs are permitted to enroll, and have these plugs replaced as necessary during the study.

6. Other Exclusion Criteria

- a. Prisoners or subjects who are involuntarily incarcerated. (Note: under certain specific circumstances a person who has been imprisoned may be included or permitted to continue as a subject. Strict conditions apply and Bristol-Myers Squibb approval is required).
- b. Subjects who are compulsorily detained for treatment of either a psychiatric or physical (eg, infectious disease) illness.

Eligibility criteria for this study have been carefully considered to ensure the safety of the study subjects and that the results of the study can be used. It is imperative that subjects fully meet all eligibility criteria.

[figure not shown]
[figure not shown]
3.3.3 *Women of Childbearing Potential*

Women of childbearing potential (WOCBP) is defined as any female who has experienced menarche and who has not undergone surgical sterilization (hysterectomy or bilateral oophorectomy) and is not postmenopausal. Menopause is defined as 12 months of amenorrhea in a woman over age 45 years in the absence of other biological or physiological causes. In addition, females under the age of 55 years must have a serum follicle stimulating hormone, (FSH) level > 40 mIU/mL to confirm menopause.

*Females treated with hormone replacement therapy, (HRT) are likely to have artificially suppressed FSH levels and may require a washout period in order to obtain a physiologic FSH level. The duration of the washout period is a function of the type of HRT used. The duration of the washout period below are suggested guidelines and the investigators should use their judgement in checking serum FSH levels.

- 1 week minimum for vaginal hormonal products (rings, creams, gels)
- 4 week minimum for transdermal products
- 8 week minimum for oral products

Other parenteral products may require washout periods as long as 6 months. If the serum FSH level is > 40 mIU/mL at any time during the washout period, the woman can be considered postmenopausal.

Double-blind Period

Subjects are permitted to continue oral corticosteroids at doses of less than or equal to prednisone 10 mg daily (or equivalent) provided that the dose is stable for at least 4 weeks prior to randomization and remains stable throughout the double-blind period. During the double-blind period, decrease in dose or discontinuation of oral corticosteroids is permitted only for adverse events or intolerance. IM, IV, SC and intra-articular corticosteroids are not permitted. Topical corticosteroids are permitted throughout the study.

Open-label Period

During the open-label period, oral corticosteroids at a dose of prednisone, up to 10 mg daily, or equivalent, may be initiated. The dose of oral corticosteroids may be decreased for any reason, but the dose may not be increased above prednisone 10 mg daily (or equivalent). Intra-articular corticosteroids are permitted, but IM, IV and SC corticosteroids are not permitted. Topical corticosteroids are permitted throughout the study.

Analgesics and NSAIDs:

- NSAIDs and analgesics (including topical NSAIDs) are not permitted within 12 hours before a joint assessment
- During the double-blind period for subjects on study therapy, NSAID doses should remain stable, as assessed by the Investigator, with the exception of decreases being permitted due to related AEs, such as gastric toxicity.
- Analgesics
 - Acetaminophen (paracetamol) permitted if
 - ◆ Average dose of ≤ 3 g/day
 - ◆ No single dose exceeding 1 g

NOTE: combination products including acetaminophen and narcotic analgesics (eg, acetaminophen with codeine phosphate, acetaminophen with propoxyphene napsylate, acetaminophen with oxycodone HCl, acetaminophen with hydrocodone bitartrate, etc.) are allowed provided the acetaminophen component dosage is accounted for in the maximum of 3 g/day.

- Narcotic analgesics must not exceed 30 mg/day of morphine or its equivalent.
- Tramadol, gabapentin, and pregabalin are allowed but doses must be stable throughout double blind period for subjects on study therapy.

3.4.2.1 Immunizations

There is limited information available regarding the effectiveness of immunizations in non-human primates that have been treated with abatacept. Limited data are available on the effect of therapeutic vaccinations in subjects receiving abatacept.

Due to the risk of infection, vaccination of subjects with any live vaccine is absolutely contraindicated during the study drug treatment period of the study, as is the administration of LIVE oral polio vaccine to household contacts. The Center for Disease Control Advisory Committee on Immunization Practices (CDC ACIP) recommends that subjects should not be administered a live virus vaccination for at least 3 months after discontinuing high dose corticosteroid therapy (defined as more than 20 mg of prednisone per day for more than 2 weeks). In view of the long half-life of abatacept, study subjects should not be administered a live virus vaccine for a minimum of 3 months following the last dose of study medication.

3.4.2.2 Infectious Complications

Subjects who develop significant infectious complications during the study should be treated appropriately and have study medication withheld, and restarted only when clinically resolved and the investigator considers it appropriate.

3.4.2.3 Management of Possible Acute Hypersensitivity Reactions

Hypersensitivity resulting in severe, acute allergic reactions may occur as a result of the protein nature of abatacept. As defined in a recent consensus statement,²⁵ anaphylaxis is highly likely if 2 or more of the following occur rapidly after administration of the study drug (minutes to several hours):

- Involvement of the skin-mucosal tissue (eg generalized hives; itching or flushing; swollen lips, tongue, or uvula).
- Respiratory compromise (eg, dyspnea, wheeze-bronchospasm, stridor, reduced peak expiratory flow, hypoxemia).
- Reduced blood pressure (BP) or associated symptoms (eg, hypotonia/collapse, syncope, and incontinence).
- Persistent gastrointestinal symptoms (eg, crampy abdominal pain, vomiting).

Sites must be appropriately prepared to handle medical emergencies such as severe hypersensitivity including anaphylaxis. Subjects must be rapidly assessed and stabilized at the site and transferred to an emergency facility as required. If subjects experience symptoms of severe allergic reactions at home, they should be advised to seek immediate medical attention, including a visit to the local emergency facility, as needed. The site will provide emergency contact information to the subject. A blood sample for analysis of anti-abatacept antibodies should be obtained in case of a hypersensitivity reaction.

The decision whether to continue treatment with the study drug will be left to the medical judgment of the investigator. Care should be taken to treat any acute toxicity, expeditiously,

should they occur. Adequate equipment and trained health care personnel should be available to handle medical emergencies when they occur at the site.

3.5 Discontinuation of Study Therapy

Subjects who discontinue treatment with investigational product during the Double-Blind Treatment Period must continue to be assessed for all efficacy measures and for safety at all remaining double-blind study visits through Week 24 (Day 169) (see [Table 5.1-2](#)). Those subjects who discontinue treatment with the study drug during the double-blind period will also require visits to assess safety and immunogenicity at 28 and 84 days after the last dose of study drug. If these visits fall within ± 14 days of a scheduled double-blind study visit, only an additional laboratory assessment (immunogenicity) needs to be performed at the scheduled study visit. Otherwise, the follow-up visits need to be performed.

Subjects who discontinue study drug during the Open-Label Treatment period should comply with protocol specified follow-up procedures as outlined in [Section 5](#). The only exception to this requirement is when a subject withdraws consent for all study procedures including post-treatment study follow-up or loses the ability to consent freely (ie, is imprisoned or involuntarily incarcerated for the treatment of either a psychiatric or physical illness).

Subjects MUST discontinue investigational product (and non-investigational product at the discretion of the investigator) for any of the following reasons:

- Subject's request to stop study treatment
- Any clinical adverse event (AE), laboratory abnormality or intercurrent illness which, in the opinion of the investigator, indicates that continuation of study therapy is not in the best interest of the subject
- Pregnancy
- Missed Doses:
 - During the double-blind period, any subject who misses greater than four consecutive doses or greater than eight total doses must be discontinued from study therapy
 - During the open-label period, any subject who misses greater than six consecutive doses or greater than ten total doses must be withdrawn from the study
- Significant non-compliance with protocol (ie, procedures, assessments, medication, etc). The investigator should discuss such issues with the BMS Medical Monitor.
- Use of prohibited medication. The investigator should discuss the use of a prohibited medication with the Medical Monitor prior to withdrawing a subject from study therapy

In the case of pregnancy, the investigator must immediately notify the Sponsor or designee of this event. In most cases, the study drug will be permanently discontinued in an appropriate manner (eg, dose tapering if necessary for subject safety). Please contact the Sponsor or designee within 24 hours of awareness of the pregnancy. If the investigator determines a possible favorable benefit/risk ratio that warrants continuation of study drug, a discussion between the investigator and the Sponsor or designee must occur.

The reason for discontinuation of study drug must be documented in the subject's medical records and entered on the appropriate case report form (CRF) page.

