3.1.4 Post-Treatment Follow-up Period

Subjects who discontinue treatment of study drug during the open-label period or complete the study will have two follow-up visits 28 and 84 days after the last treatment visit, to perform safety and laboratory assessments, including immunogenicity testing. Subjects who discontinue treatment with the study drug during the double-blind period will require two visits to assess safety and immunogenicity 28 and 84 days after the last dose of study drug. If these visits are within ± 14 days of a scheduled study visit, only an additional laboratory assessment (immunogenicity) needs to be performed at the scheduled study visit. Otherwise, the follow-up visits as described in the Time & Events table ([Table 5.1-6](#)) need to be performed.

The start of the trial is defined as the date the first subject signs the informed consent. End of trial is defined as the last visit or scheduled procedure shown in the Time & Events schedule for the last subject. The study will continue beyond primary endpoint collection until the End of Trial.

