3.6 Discontinuation from the Study

Subjects MUST discontinue the study for any of the following reasons:

- Termination of the study by Bristol-Myers Squibb (BMS)
- Loss of ability to freely provide consent through imprisonment or involuntarily incarceration for treatment of either a psychiatric or physical (eg, infectious disease) illness
- Subject withdraws consent
- Participation in another clinical trial with an investigational product

The reason for discontinuation from the study must be documented in the subject's medical records and entered on the appropriate case report form (CRF) page.

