3.7 Post Study Drug Study Follow up

Subjects who discontinue study drug may continue to be followed.

Subjects who withdraw consent (according to Section 3.7.1) or are lost to follow-up (according to Section 3.7.2) will not be followed in this study; all other subjects will continue to be followed for collection of follow up data as required and in line with [Section 5](#), Study Assessments and Procedures.

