5.3 Safety Assessments

On Day 1, the results of all assessments must be reviewed to ensure that eligibility requirements are met before contacting the Central Randomization System for the subject's randomization assignment.

Subjects who terminate treatment early should complete the appropriate Early Termination Visit and the Post Drug Follow-up Visits. The Early Termination Visit should be as soon as possible after the last dose of study medication.

All assessments should be performed or administered prior to study drug administration unless otherwise indicated.

Only data for the procedures and assessments specified in this protocol should be submitted to BMS on a case report form. Additional procedures and assessments may be performed as part of standard of care; however, data for these assessments should remain in the subject's medical record and should not be provided to BMS, unless specifically requested from BMS.

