According to the protocol, patients who discontinue treatment in the Double-Blind Period should continue the study off treatment up to Day 169 to be assessed for efficacy. A CRF is collecting if a subject (on or off treatment) is continuing up to Day 169 or not. The summaries detailed below will provide the reasons for discontinuation on or off treatment prior to Day 169. The summary of subject disposition for the Double-Blind Period (on and off treatment up to Day 169) will be based on the modified ITT analysis population and will summarize by treatment group the:

- number (percentage) of subjects completing the Double-Blind Period (on and off treatment combined) up to Day 169
- number (percentage) of subjects who discontinued treatment and did not continue in the study up to Day 169
- number (percentage) of subjects per reason for not continuing in the study up to day 169 (after subject discontinued the treatment)

Percentages will be based on a denominator of all randomized and treated subjects (modified ITT population). The reasons for not completing in the Double-Blind Period (on or off treatment) or for not being treated in open-label will also be listed.

The summary of subject disposition for the open-label treatment period will be based on the Open-Label Population analysis population and will summarize by treatment group the:

- number (percentage) of subjects completing the open-label period
- number (percentage) of subjects ongoing in the open-label period (i.e. entering Open-label period but not completed or discontinued at the time of lock)
- number (percentage) of subjects not completing the open-label period (i.e. early discontinued subjects)
- number (percentage) of subjects per reason for not completing the open-label period (i.e. reasons for early discontinuation)
- number (percentage) of subjects continuing in the study (i.e. entering in the follow-up period)

- number (percentage) of subjects not continuing in the study (i.e. not entering in the follow-up period)
- number (percentage) of subjects per reason for not continuing in the study

Percentages will be based on a denominator of all subjects treated in the open-label period. The reasons for not completing the open-label period or for not continuing in the study will also be listed.

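### The open-label missed-dose rule in Protocol 3.5 withdraws subjects from the study, where the rest of the protocol stops drug and keeps them in follow-up

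*Protocol*

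**What the plan says.** Protocol 3.5 lists the reasons for which a subject must stop investigational product. Two bullets deal with missed doses. In the double-blind period, "any subject who misses greater than four consecutive doses or greater than eight total doses must be discontinued from study therapy". In the open-label period, "any subject who misses greater than six consecutive doses or greater than ten total doses must be withdrawn from the study".

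The second paragraph of the same section deals with stopping drug in the open-label period: "Subjects who discontinue study drug during the Open-Label Treatment period should comply with protocol specified follow-up procedures as outlined in" Section 5. It allows only two exceptions: withdrawal of consent for all study procedures, and loss of the ability to consent freely.

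Three other sections point the same way:
- Protocol 3.1.4: "Subjects who discontinue treatment of study drug during the open-label period or complete the study will have two follow-up visits 28 and 84 days".
- Protocol 3.7, after setting aside subjects who withdraw consent or are lost to follow-up: "all other subjects will continue to be followed for collection of follow up data as required".
- Protocol 5.3: "Subjects who terminate treatment early should complete the appropriate Early Termination Visit and the Post Drug Follow-up Visits".

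Leaving the study is covered separately in 3.6, which opens "Subjects MUST discontinue the study for any of the following reasons" and gives four reasons. Missed doses are not one of them.

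**The concern.** One bullet orders a subject out of the study in a section that otherwise deals with stopping drug, and it conflicts with the follow-up rule a few lines above it. The bullet says must, the follow-up paragraph says should, and 3.7 opens by saying that subjects who stop drug may be followed. A coordinator looking for the specific rule on missed open-label doses would find an instruction to withdraw the subject.

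The visits at stake are those in Table 5.1-6: adverse event assessment, pregnancy test, anti-abatacept antibodies and a PK sample. Antibody positivity during the cumulative abatacept period and three months of follow-up is a secondary endpoint in Protocol 8.3.2, so a lost visit is also lost endpoint data.

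**Working it through.** **The texts side by side**

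| Place | Consequence for the subject |
|---|---|
| 3.5, heading of the list | Stop investigational product |
| 3.5, double-blind missed doses | Stop study therapy |
| 3.5, open-label missed doses | Withdrawn from the study |
| 3.5, second paragraph (open-label) | Follow-up applies; two exceptions, neither of them missed doses |
| 3.1.4 | Two follow-up visits |
| 3.6 | Four reasons to leave; missed doses not listed |
| 3.7 | Followed unless consent is withdrawn or contact is lost |
| 5.3 | Early termination visit and follow-up visits |

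Only the third row removes the subject from the study for missed doses.

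**What would still lie ahead when the rule triggers**

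Inputs:
- Weekly dosing with a window of ±3 days; a dose outside its window is skipped (Protocol 4.5.2.1 and 5.1.3).
- Triggers: the 7th consecutive miss or the 11th miss in total (Protocol 3.5).
- Follow-up visits 28 and 84 days after the last dose (Table 5.1-6, footnote a).
- SAE collection for 84 days after dosing stops (Protocol 6.1.1).
- Open-label visits every 28 days (Table 5.1-3).

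I count a dose as missed when its +3-day window closes. Let *d* (from −3 to +3) be the day on which the last dose was taken relative to its target. After a final run of *r* misses, days since the last dose = 7*r* + 3 − *d*, which runs from 7*r* to 7*r* + 6. SAE days left = 84 minus that number.

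| Final run *r* | Days since last dose | SAE days left | Visits still ahead |
|---|---|---|---|
| 1 | 7–13 | 71–77 | 28-day and 84-day |
| 2 | 14–20 | 64–70 | 28-day and 84-day |
| 3 | 21–27 | 57–63 | 28-day and 84-day |
| 4 | 28–34 | 50–56 | 84-day (28-day visit due or past) |
| 7 | 49–55 | 29–35 | 84-day |

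*Consecutive rule* (*r* = 7). With *d* = +3, 0 and −3, the last dose was 49, 52 and 55 days earlier, leaving 84 − 49 = 35, 84 − 52 = 32 and 84 − 55 = 29 SAE days. These are maxima, because they assume that the 7th miss is recognised as soon as its window closes. If recognition waits up to 28 days for the next visit, the range falls to as little as 29 − 28 = 1 to 35 − 28 = 7 days. The 56-day summary window in Protocol 8.4.3 is nearly over even with prompt recognition: 56 − 55 = 1 to 56 − 49 = 7 days remain.

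*Total rule.* Weekly targets from Day 169 to Day 351 number (351 − 169)/7 + 1 = 27, or 28 if the Day 358 target is given early within its window. The 11th miss is then 11/28 = 39% to 11/27 = 41% of doses. The 11th miss need not end a long run. If it ends a run of one to three, the last dose was 7 to 27 days earlier and both visits are still to come.

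One uncertainty remains in the clock. Protocol 3.1.4 counts from the last treatment visit, not the last dose. Depending on which visit is meant, the 28-day visit could also still be ahead under the consecutive rule. The SAP's follow-up schedule belongs to a later protocol version, so its visit days are not used here.

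**The case against.** The best defence is that the protocol resolves the wording itself. The list is headed as reasons to stop drug, and the second paragraph of 3.5 closes its exceptions expressly. To skip follow-up, a site would have to disregard a clause in the same section. There is also a harmless reading. A double-blind stopper stays on the visit schedule to Day 169, whereas an open-label stopper has no such duty and moves to follow-up, so leaving the study may only mean leaving the open-label visits. Footnote b to Table 5.5.1-1 supports this, since it describes subjects as off study while scheduling their 28- and 84-day samples. Section 3.6 is weak evidence either way: it also omits loss to follow-up, so it is not plainly exhaustive.

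Much of this stands, and it makes a slip the likeliest explanation. It does not make the bullet correct: the instruction is mandatory, and the harmless reading has to be pieced together from other sections.

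A reader might infer more than the documents support, in three ways:
- *That safety surveillance ends for these subjects.* It does not. The SAE duty in 6.1.1 runs from the end of dosing whatever the subject's study status. What could be lost is the scheduled visit that supports it.
- *That the SAP confirms removal from follow-up*, because SAP 7.3.1 counts the "number (percentage) of subjects not continuing in the study (i.e. not entering in the follow-up period"). That is a label in a disposition table, and the follow-up paragraph of the same section includes open-label discontinuers among those expected to enter follow-up.
- *That the efficacy result is exposed.* The bullet applies only in the open-label period, after the Day 169 primary and key secondary assessments.

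**Conclusion.** The inconsistency is real and minor. One bullet uses study withdrawal where the surrounding text requires treatment discontinuation. Read literally, it puts the 84-day visit at risk under the consecutive rule and possibly both visits under the total rule. The reach is limited to open-label and cumulative-abatacept safety and immunogenicity data.

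The day counts rest on the missed-dose convention above and on counting visits and SAE days from the last dose. The documents give no basis for estimating how many subjects would trigger the rule or how many sites would apply it literally.

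Confidence is medium, because the wording may already have changed. The protocol history supplied runs to Amendment 01 (25 August 2016), and SAP 2.4 lists a 13 March 2017 amendment whose purposes included clarifying the criteria for stopping study therapy.

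**What to change.** First check the text of the 13 March 2017 amendment. If it already corrected this bullet, nothing further is needed. Otherwise, in the open-label missed-dose bullet of Protocol 3.5, replace *withdrawn from the study* with *discontinued from study therapy*. The existing follow-up rules then apply without further edits.

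The cost is one phrase. It adds no visits, since the follow-up visits are already scheduled for other subjects who stop open-label drug, and it changes no analysis.
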